Exploratory Study on Effect of Whitening Agent with Emulsion Gel in Xerostomic Population

Principal Investigator: [name], DMD, MS

Co-Investigators: [name], DMD, PhD

Study Coordinators:

[name], AS, CDA, CCRP

[name], BS, CCRP

[name], RDH [name]

Study Location: Tufts University School of Dental Medicine

[name]

Sponsor: Procter & Gamble

Protocol Version Date: 4/14/2023

Exploratory Study on Effect of Whitening Agent with Emulsion Gel in Xerostomic Population [name], DMD, MS

I) Introduction

A) Aim/Hypothesis/Objective

Objectives:

- Primary aim: To see a reduction in the self-reported subjective perception of dryness in the oral cavity.
- Secondary aims: To measure self-reported sensitivity of the teeth, self-reported
 perception of teeth whiteness, and objective measurement of improvement of saliva
 production.

II) Background and Rationale

Xerostomia, is a subjective sensation of dryness of the mouth, which may have a significant effect in a persons quality of life. The sensation of dryness of the mouth may be caused by autoimmune diseases which attack the saliva producing glands irreversibly e.g., salivary glands, or the sensation of dryness could be caused by therapeutic radiation, which can destroy the salivary glands at the genetic level and impede their functions. Additionally, there are more than 700 medications including antihypertensives, anti-anxiety agents, psychiatric remedies, and antihistamines that can effect neural transmission. Neural transmission is when the neuro transmission is hindered reversibly leading to the salivary hypofunction that results in dry mouth. It is estimated that 12-47% of the elderly and 10-19.3% in their early 30's suffer from dry mouth (6)(7). In a study, it was found that the prevalence of xerostomia was 10.0% (with no apparent gender difference) among 32-year-olds and was significantly higher among those taking antidepressants (odds ratio =4.7) (5). At risk groups may present much higher (60+%) rates of xerostomia. A systemic literature review suggests a prevalence of 27 –32% of the medicated population suffer from xerostomia as a side effect (7).

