The investigational product to be used in this study is manufactured by P&G and called, "Crest Whitening Emulsions". The amount of each dose should be enough to cover the entire tip of the whitening wand, approximately ½ a tsp. The use of the study product in this study will be for what they are approved for. Per the manufacturer's instructions, study subjects will be asked to apply the study product up to 4 times a day.

Procter and Gamble will be supplying the study product gel to the study team. IDS will not be involved in this study.

The investigative product to be used in this study is a hydrophobic emulsion containing agent (a teeth whitening gel with emulsification gel). It contains:

Petrolatum, Water, Hydrogen Peroxide, Flavor, Sucralose, Sorbitan Palmitate

D) Subject Characteristics

- 1) Inclusion Criteria
 - At least 18 years of age.
 - The inability to produce more than < 0.18mL/min of unstimulated saliva.
 - Score of 5 or more on question 1 of the VAS dry mouth scale (How severe is your dryness right now?), evaluated in the Pre-Product Use Dry Mouth & Sensitivity Questionnaire .
 - Evidence of currently taking Xerostomia-inducing medication such as, antihypertensives, anti-anxiety agents, psychiatric remedies, antihistamines.
 - Subject not currently using any teeth whitening or desensitizing products
 that contain potassium nitrate such as Sensodyne or Pronamel.
 - Subject willing to comply with the study regimen and products.

2) Exclusion Criteria

- Subjects who are currently pregnant (self-reported).
- Subjects able to produce more than 0.18mL/min of unstimulated saliva

- Subjects that have ever received therapeutic radiation in the head and neck area.
- Subjects with a diagnosis of conditions that would affect salivary flow such as Sjogren's Syndrome.
- Subjects with a condition the investigator believes not suitable for the study such as autoimmune diseases that impact salivary flow.
- Subjects that currently use whitening toothpaste, desensitizing toothpaste, or any other products causing similar results.
- Subjects currently participating in any other research studies.
- Subject unable to provide consent (ex. Cognitively impaired adults).
- Non-English speaking

3) Subject Withdrawal/Termination Criteria

- Subjects who do not comply with the study procedures, such as use of teeth whitening products, may be withdrawn from the study.

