- The study team may terminate subjects if they no longer fulfill inclusion criteria, if an exclusion criterion is met, or if they do not show up for scheduled study visits.
- Subjects who experience an unanticipated adverse drug effect will be withdrawn from the study.
- Subjects unable to complete the study procedures due to a medical condition such as dry mouth and sensitivity conditions that result in the inability to capture meaningful data during the study procedures.
- Subjects may choose to withdraw from the study at any time.

Subjects may remain patients of TUSDM if they decide to withdraw from the study or are withdrawn by the study team.

If during the course of their participation in the study, a subject chooses to withdraw or is withdrawn by the research team, any data that has been

collected will not be included in the analysis and the subject will be asked to return any leftover whitening gel and the diary. The subject is able to keep the toothpaste and toothbrush.

Subjects will not be able to partially withdrawal from study intervention and just be involved with continued data collection.

The Principal Investigator will determine whether subjects (either withdrawn subjects or subjects completing the study) are in need of additional treatment and/or follow-up observation as a result of participation in this trial and will refer them to their primary care provider for further care. Subjects and/or their insurance will be responsible for the cost of any standard of care follow-up visits or additional treatment that is not part of this study.

4) Vulnerable Populations

Transgender subjects will be recruited as part of this study. All subjects will be asked on the Medical/Dental History Form to identify their sex, to which they will answer however they choose. They will not be sought out or targeted for participation and will not be discriminated against as a result of their sexual orientation/gender identity. The subjects will not be asked to disclose if they are transgender or not on the Medical/Dental History Form.

Cognitively impaired adults and pregnant adults will not be enrolled in this study. There would be no direct benefits to these specific vulnerable populations by enrolling them. Pregnancy will be determined through self-reporting.

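### A withdrawal ground that names dry mouth and tooth sensitivity, together with deletion of withdrawn subjects' data, can remove poor outcomes from the analysis

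*Combined protocol and SAP*

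**What the plan says.** Section III.D.3 (Subject Withdrawal/Termination Criteria) lists among its grounds that a subject cannot finish the procedures, where the cause is a "medical condition such as dry mouth and sensitivity conditions that result in the inability to capture meaningful data during the study procedures". It does not say what makes data meaningful. The bullet also has no verb, so it is unclear whether withdrawal is required or discretionary.

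Two further statements in III.D.3 settle what follows. Data from a subject who withdraws or is withdrawn that have been "collected will not be included in the analysis". And "Subjects will not be able to partially withdrawal from study intervention and just be involved with continued data collection".

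Section I.A gives the primary aim as "To see a reduction in the self-reported subjective perception of dryness in the oral cavity"; tooth sensitivity and saliva production are among the secondary aims. Section III.E.1 lists tooth sensitivity as a standard risk of whitening products. For entry, III.D.1 requires "The inability to produce more than < 0.18mL/min of unstimulated saliva" and a score of at least 5 on the first dryness VAS question. The flow exclusion in III.D.2 confirms that 0.18 mL/min is an upper limit. No lower limit on flow and no upper limit on the VAS is set.

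**The concern.** The two conditions named as examples of a reason to withdraw are what the trial measures. Dry mouth is also the entry condition, and sensitivity is an expected effect of the product. Withdrawal on this ground is therefore likely to be related to outcome: those most exposed to it are subjects whose dryness has not improved or whose teeth have become sensitive.

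On its own the bullet would cost only the measurements that could not be taken. The deletion sentence extends the loss to everything the subject has contributed. With one arm, no blinding and about 25 subjects, there is no comparison group to show or offset a selective loss, and unblinded staff decide who meets the ground. At stake is whether the reported changes in dryness, sensitivity and flow describe all treated subjects or only those who did well enough to stay.

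**Working it through.** **1. The plan's own figure.** Section III.B gives 25 subjects, without alpha, power, effect size or SD, so it cannot be reproduced. It is used below as the number treated. For scale, a paired t test on 25 subjects at two-sided 0.05 has 80% power for a standardised change of 0.58 (alpha and power assumed).

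**2. When the ground can act at Visit 2 (III.F).** Withdrawal criteria are reviewed at step 3. Saliva Collection 1 is step 6, the questionnaire step 7, the application step 8 and Saliva Collection 2 step 9.
- Withdrawn at step 3: no Visit 2 values are taken, and the Visit 1 values are deleted.
- Unable to apply the gel at step 8: pre-product flow and pre-product dryness and sensitivity answers already exist, and they are deleted with the Visit 1 values.

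**3. The empty vial.** The limit of 0.18 mL/min over 5 minutes gives 0.18 × 5 = 0.9 mL at most, with no minimum. Very small or empty collections are foreseeable. Flow is a weight difference, so zero can be recorded, but no rule says that it must be.

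**4. Flow illustration.** Assumed: 25 treated, k removed, and the rest gain 0.02 mL/min, so the reported gain is 0.020. The gain over all 25 is [(25 − k) × 0.02 + k × c] / 25, where c is the change in each removed subject.

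| k | c = 0 (stays at 0) | overstated by | c = −0.05 (falls from 0.05 to 0) | overstated by |
|---|---|---|---|---|
| 1 | 0.48/25 = 0.0192 | 4% | 0.43/25 = 0.0172 | 16% |
| 2 | 0.46/25 = 0.0184 | 9% | 0.36/25 = 0.0144 | 39% |
| 3 | 0.44/25 = 0.0176 | 14% | 0.29/25 = 0.0116 | 72% |

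The overstatement is 0.020 divided by the all-subject gain, minus 1; for example 0.020/0.0172 = 1.16.

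**5. Effect on the test, in SD units of change, for any of the three endpoints.** 200,000 simulated trials of 25 subjects, normally distributed changes, true mean change 0. k subjects are removed and the rest tested with a one-sample t test at two-sided 0.05. A false benefit is a significant result in the favourable direction. With nobody removed the rate is 2.5%.

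| k | k worst removed: bias (SD) | false benefit | removal correlated 0.5 with change: bias (SD) | false benefit |
|---|---|---|---|---|
| 1 | 0.083 | 7.1% | 0.041 | 4.1% |
| 2 | 0.153 | 14.2% | 0.076 | 5.9% |
| 3 | 0.217 | 23.6% | 0.108 | 7.8% |

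Removing exactly the worst subjects is the extreme case; the correlation of 0.5 is a milder one.

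**The case against.** The strongest reply is that the trigger is not a bad value. The bullet requires that the subject cannot complete the procedures and that meaningful data cannot be captured. A high dryness or sensitivity score that can be marked on the form remains an outcome. This stands. A reader might infer that the worst scores automatically become withdrawals, and the text does not say that.

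A reader might also infer that zero saliva is a withdrawal ground. No section says so. Someone who drools nothing for five minutes has completed the procedure, zero flow is eligible, and the weighing can record it. What remains is narrower: with dry mouth named as an example and the key term undefined, the text does not rule out treating an empty vial as no usable result.

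Third, the deletion sentence does most of the damage, and striking the two examples alone would still leave any medical condition as a ground. Both points are right, so the remedy has to reach the deletion sentence.

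Fourth, a subject at zero flow at baseline cannot fall further, so removing that subject need not hide a decline. This is why the range in step 4 starts at 4%.

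**Conclusion.** The concern holds in this form: the withdrawal ground, the deletion of collected data and the bar on continued collection together allow subjects who do badly on dryness or sensitivity to disappear from the analysis. This can bias the dryness, sensitivity and flow results toward benefit.

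The size cannot be determined, because the documents give no expected withdrawal rate and no variability. Under the stated assumptions, losing 1 to 3 of 25 subjects overstates the flow gain by 4% to 72%, depending on what happened to those removed. It raises the false-benefit rate from 2.5% to 4.1%–7.8% when removal is moderately related to outcome, and to 7.1%–23.6% when the worst subjects are the ones lost. The largest bias in step 5, 0.217 SD, is about 37% of the 0.58 SD in step 1 (0.217/0.584). The removal counts, the flow changes, the normal distribution and the correlation are all assumed.

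The documents do not support saying that every result is affected: perceived whiteness is also a secondary aim and has no shown link to this ground. Nor do they show that sites would apply the bullet in this way, only that they could.

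**What to change.** Data and analysis rules are enough:

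- Reword the bullet in III.D.3 so that dryness, low or zero flow and tooth sensitivity are not in themselves reasons to discard data, and define what counts as meaningful data.
- State in III.F that an empty vial is recorded as 0 mL/min, and in III.B that extreme VAS scores are valid values.
- Amend the deletion sentence so that all values obtained before withdrawal are kept and analysed. This includes pre-product values at a visit where the application does not take place, with the reason recorded.
- Reconcile the bar on continued data collection with that rule, so that staff know which measurements of a visit in progress still count.
- In III.B, report withdrawals by reason and by visit, and add a sensitivity analysis that assigns unfavourable values to withdrawn subjects, such as 0 mL/min for flow and the worst end of the VAS.

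The cost is a few sentences in an amendment, a check that the consent form agrees on keeping data, and one extra analysis. No new procedure is needed. The downside is small: some zero flows in the data and some missing post-application values.

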The product being used is a commercially available product, known as "Crest Whitening Emulsions", will be used as the investigative product. There will be no active control group. This is not the first time P&G whitening gel will be used in humans. We do believe this is the first study investigating dry mouth sensation from using a whitening gel.

- III) Research Plan
 - A) Experimental Design

This will be a single center, two visit study investigating the effectiveness of dryness in the oral cavity, whiteness of teeth, and teeth sensitivity after one week's use of whitening agent.

B) Sample Size and Statistical Analysis

Sample size

This is a single site study. All study-related procedures will take place at TUSDM. Based on our preliminary data from a previous study, we anticipate 25 subjects will be needed to achieve the necessary statistical power required to observe expected differences in relief of dryness in the oral cavity. Because we anticipate the potential of many screen failures due to the VAS scale and saliva production requirements outlined in the exclusion/inclusion criteria section, we will screen/enroll a total of 100 subjects to conservatively account for potential dropouts or screening failures.

Statistical analysis

The subjects will be asked to complete one questionnaire each visit. Completing the first part before the application of the study product, and completing the second part after the application of the study product, as directed on the questionnaire. The self-reported scores from the visual analogue scales (VAS) will be considered on the first and final visit. The salivary flow before and after the application of the product, Pre & Post-Product Use Dry Mouth & Sensitivity Questionnaire before and after the product application will be compared using a student -t test method. The same method will be used to make comparisons of these gathered data points between the first and final visits.

Randomization

This will be an open label study; thus no randomization plan is necessary.

Blinding

There will be no blinding for this study.

C) Products

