- The subjects will be asked to read the informed consent form (ICF). Subjects will
 be given ample time to have any questions answered. If a subject decides to
 participate, he or she will be asked to sign the ICF. A copy of the ICF will be given
 to the subject.
- 3. Subject will be asked to complete demographic information and a medical history.
- 4. An oral exam, including evaluation of oral cavity, soft and hard tissues, will be completed following standard of care procedures in US dentistry using a mouth mirror and dental explorer.
- 5. Subject medications with potential side effects being dry mouth will be verified using the Physician's Reference Desk.
- 6. Saliva Collection 1 (pre-product application): Saliva will be collected by asking subjects to do nothing but drool into a pre-weighed vial for 5 minutes (referred to as the Drooling Method). The post collection weight will be subtracted from the pre-weight to determine the flow rate. The saliva samples will be discarded after they are weighed.
- A paper questionnaire will be given to subject to complete before application of study product and after application of study product. Questionnaire includes Visual Analogue Scale (VAS) questionnaire on dry mouth, quantity of saliva, and perceived sensitivity of teeth.

- 8. Inclusion/exclusion criteria will be evaluated and eligibility for the study will be determined.
- 9. Demonstration and application of study product:
 - a. A visual and oral demonstration of application of the whitening gel will be performed by a study team member. The script for the demonstration will be the one provided in the information packet in each study product box so the subject can bring the instructions home. The study team member will mimic the necessary steps to properly apply the gel, without using the product. The study team member will then have the subject complete the steps while applying the gel to their own teeth. Subjects will then be asked to sit for 5 minutes to let the gel set on their teeth.
- 10. Saliva Collection 2 (post-product application): Saliva will be collected using the same Drooling Method as Saliva Collection 1. The saliva samples will be discarded after they are weighed.

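### Discarding all data from withdrawn subjects loses complete Visit 1 before/after pairs, and the loss may be related to outcome

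*Combined protocol and SAP*

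**What the plan says.** **The rule.** Section III.D.3 (Subject Withdrawal/Termination Criteria) applies whether the subject chooses to leave or is removed by the team. Any data gathered up to that point and "collected will not be included in the analysis and the subject will be asked to return any leftover whitening gel and the diary". The same section rules out stopping the product while continuing data collection. The documents define no other analysis set, no method for missing data and no sensitivity analysis.

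**The reasons for withdrawal or termination** in the same section include:
- Missed visits: the team may terminate subjects "if they do not show up for scheduled study visits".
- Loss of eligibility: "The study team may terminate subjects if they no longer fulfill inclusion criteria, if an exclusion criterion is met".
- Inability to complete procedures "due to a medical condition such as dry mouth and sensitivity conditions that result in the inability to capture meaningful data".
- Adverse effects: "Subjects who experience an unanticipated adverse drug effect will be withdrawn from the study".

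**What Visit 1 provides.** Section III.F, Visit 1, has a first saliva collection at step 6. At step 7, "A paper questionnaire will be given to subject to complete before application of study product and after application of study product". At step 10, after application, "Saliva will be collected using the same Drooling Method as Saliva Collection 1".

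**What is analysed.** Section III.B (Statistical analysis) compares "The salivary flow before and after the application of the product", and the before and after questionnaires, by Student's t test. It then applies the same method between the first and final visits. Section III.B (Sample size) sets 25 subjects as the number needed and plans to screen/enrol 100 to allow for dropouts and screening failures.

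**The concern.** The exclusion rule is broader than the analysis requires. The within-visit comparison uses measurements taken minutes apart at one visit, so a missing Visit 2 is no reason to drop the Visit 1 pair. The clearest case is a subject terminated for not attending Visit 2. There are only two visits, so that subject has already completed Visit 1.

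The second issue is selection. Dryness is the primary outcome and tooth sensitivity a secondary one (section I.A), and conditions of both kinds appear among the withdrawal reasons. Entry also depends on a dryness VAS of 5 or more and on flow not above 0.18 mL/min (section III.D.1 and III.D.2), both of which are also outcome measures. If those thresholds were applied again, subjects who improved could be removed. If subjects with adverse effects or poor response were removed, the opposite would happen. In a single-arm study no comparison group would reveal or offset either effect.

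**Working it through.** **1. Does a withdrawn subject have usable data?** Steps 6, 7 and 10 of Visit 1 give flow and VAS before and after application. Section III.B plans the before/after test on exactly these. Anyone who leaves after completing Visit 1 therefore has complete pairs. Anyone who leaves before the post-application measurements does not.

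**2. Can exclusion depend on outcome?**
- *Dry mouth or sensitivity conditions:* yes, by the wording of the reason itself. The affected visit may have no measurements, but an earlier Visit 1 pair would still be dropped.
- *Unanticipated adverse effects:* possibly. Withdrawal is mandatory, but tooth sensitivity is a listed risk (section III.E.1), so expected sensitivity does not by itself trigger it.
- *Loss of eligibility:* uncertain. Termination is optional. The Visit 2 review of eligibility (step 3) comes before that visit's saliva collection and questionnaire (steps 6 and 7). The schedule table marks a review of eligibility and withdrawal criteria at Visit 2, but marks the evaluation of eligibility criteria at Visit 1 only. The documents do not say whether the VAS and flow limits are applied again.

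**3. Inputs for size.** From the plan: n = 25. The 25 cannot be reproduced, because alpha, sidedness, power, effect size, SD and dropout rate are not given. Assumed here: a paired two-sided 5% t test (the plan does not say paired), 80% power at n = 25, and 2 to 5 subjects lost after Visit 1 and not replaced.

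**4. Precision.** The 95% CI half-width, in SDs of the change, is t(0.975, n−1)/√n. At n = 25 this is 2.064/5 = 0.413.

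**5. Power.** By the noncentral t distribution, 80% power at n = 25 corresponds to a change of 0.584 SD. The table gives the power for that change at smaller n, and the change detectable with 80% power.

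| Pairs kept | Half-width (SD) | Widening | Power for 0.584 SD | Detectable at 80% (SD) |
|---|---|---|---|---|
| 25 | 0.413 | – | 80% | 0.584 |
| 24 | 0.422 | 2.3% | 78.2% | 0.597 |
| 23 | 0.432 | 4.8% | 76.3% | 0.611 |
| 22 | 0.443 | 7.4% | 74.3% | 0.626 |
| 20 | 0.468 | 13.4% | 69.8% | 0.660 |

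**6. Selection.** For an excluded fraction f, mean(kept) − mean(all) = f × [mean(kept) − mean(excluded)]. With f = 2/25 = 0.08 to 5/25 = 0.20, an assumed 1 SD difference shifts the mean by 0.08 to 0.20 SD, against a half-width of 0.413 SD.

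**7. Effect on false positives (illustration).** With no true change and 5 of 25 subjects removed on a tendency correlated with outcome, the simulated two-sided type I error is about 4.9%, 7.6% and 12.7% at correlations of 0, 0.3 and 0.5. With no correlation, only precision is lost.

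**The case against.** The strongest reply is that the study plans to screen/enrol 100 subjects partly to cover dropouts, so a fall in power from 25 to 20 pairs describes a situation the plan anticipates. Attrition may also be small: there are two visits about a week apart, a reminder call and a payment at each visit. With one loss the interval widens by only 2.3%. Termination for a missed visit is optional, and the text says terminate where the data rule says withdrawn. A subject who misses Visit 2 has no final-visit data under any rule, so the comparison over one week's use gains nothing for that subject. The study is labelled exploratory.

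Much of this stands as a limit on size. The power figures hold only if losses are not replaced, and the repair is mainly to the Visit 1 comparison. It does not remove the point. Additional subjects can restore the number but not the particular people excluded. A termination decided by the team, under a heading that covers both terms, is most naturally read as a withdrawal by the team. The 100 is shared between screening failures and dropouts, with no dropout rate given.

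**Conclusion.** The concern holds and should be fixed. The rule as written discards valid Visit 1 pairs without an analytic reason, and the exclusion may be related to outcome. On the assumptions above, the cost is a 5% to 13% wider interval and a drop from 80% to between 76% and 70% power if losses are not replaced. Any selection would add 0.08 to 0.20 SD of shift per 1 SD difference between kept and excluded subjects. These are modest amounts. The direction cannot be determined from the documents: removing poor responders would overstate benefit, and removing improvers would understate it. Confidence in the finding is high because it rests on the wording of the rule rather than on the assumed figures.

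**What to change.** Replace the sentence in section III.D.3 with wording such as:

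> Data collected up to withdrawal are retained and analysed, as consent allows. Visit 1 pre/post comparisons use all subjects who applied the gel at Visit 1 and have both measurements. Visit 1 to Visit 2 comparisons use all subjects with Visit 2 data, including any withdrawn afterwards, with a sensitivity analysis for missing Visit 2 data. Withdrawals are reported by reason. Visit 2 VAS and flow values are not used to decide inclusion in the analysis.

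The method of the sensitivity analysis should be named in advance. One simple choice is to repeat the comparison with missing Visit 2 scores set to no change, and then to a range of less favourable values. Read literally, the present rule also covers safety data, so the new text should say that safety summaries include everyone who applied the gel.

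This changes who is analysed, not who is withdrawn. It restores the Visit 1 comparison for subjects who have both measurements and whose consent allows retention. It cannot recover Visit 2 scores that were never taken. The cost is protocol wording, a little more analysis and matching consent language (the consent form was not available to check). No subjects, visits or procedures are added. The downside is that the estimates may turn out less favourable.
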